6.5 Safety Analysis

All safety analyses will be summarized based on the Safety population.

Potentially clinically significant (PCS) abnormalities will be defined according to the Akros Safety Reporting Standards as of 18 Oct, 2004. The PCS values for vital signs, ECG and laboratory data will be flagged in data listings.

Treatment-emergent PCS abnormalities are values that meet the specified criteria after the initiation of study drug (see Section 10.1 for detailed clinically significant criteria).

Treatment-emergent PCS values will be summarized, presenting the number and percentage of subjects who had at least one PCS value on or after the first dose of study drug (JTE-451 or placebo). The denominator is always the number of subjects in the safety population, regardless of whether the subject had any post-baseline measurements. The numerator is the number of subjects in the safety population with any PCS value in the treatment-emergent period. Note that for the purpose of determining PCS abnormalities, baseline is always the last non-missing value before the first dose of study drug. As all procedures will be performed before dosing at each scheduled visit, the values of the scheduled Day 1 collection will be baseline and will not be treatment-emergent PCS.

All safety data will be presented in the data listings, and will be flagged for events of interest (e.g., out of range laboratory data) as appropriate.

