10. APPENDICES

10.1 General Clinically-Significant Criteria for Safety Parameters

Parameter (Full Names)	Reporting Unit	Clinically Significant Criteria ¹	
		Low	High
Hematology			
Hematocrit	%	Male ≤37% Female ≤32%	NA
Hemoglobin	g/dl	Male ≤11.5 Female ≤9.5	NA
White blood cell	E3/mm ³	≤2.8	≥16.0
Platelets	E3/mm ³	≤75	≥700
Mean corpuscular hemoglobin	pg/cell	--	--
Mean corpuscular hemoglobin concentration	g/dl	--	--
Mean corpuscular volume	fL	--	--
Red blood cell	E6/mm ³	≤3.5	NA
Differential			
Bands or (Band neutrophil (stab))	%	NA	≥10%
Basophil (absolute)	E3/mm ³	NA	≥0.4
Basophil (%)	%	NA	≥5%
Lymphocytes (absolute)	E3/mm ³	≤0.5	≥4.5
Lymphocytes (%)	%	≤10%	≥80%
Monocytes (absolute)	E3/mm ³	NA	≥1.5
Monocytes (%)	%	NA	≥ 20%
Neutrophils (absolute)	E3/mm ³	≤1.0	
Neutrophils (%)	%	≤15%	≥90%
Eosinophils (absolute)	E3/mm ³	NA	≥0.7
Eosinophils (%)	%	NA	≥10%
Coagulation			
Prothrombin time	seconds	NA	≥16
International Normalized Ratio	ratio	NA	≥2.00
Partial thromboplastin time	Seconds	NA	≥50

¹ Can be revised as appropriate, but should be consistent within the project.

Parameter (Full Names)	Reporting Unit	Clinically Significant Criteria ¹	
		Low	High
Heart Function			
Aspartate transaminase	IU/l	NA	≥3 x UNL
Lactic dehydrogenase	U/L	NA	≥3 x UNL
CPK (MB Fraction)	µg/L	--	--
Liver Function			
Alkaline Phosphatase	IU/l	NA	≥3 x UNL
Alanine transaminase	IU/l	NA	≥3 x UNL
Total Bilirubin	mg/dl	NA	≥2.0
Gamma-glutamyltransferase	IU/l	NA	≥3 x UNL
Total Protein	g/dl	≤4.5	≥9.0
Albumin	g/dl	≤2.5	≥6.5
Renal Function			
Blood urea nitrogen	mg/dl	NA	≥30
Creatinine	mg/dl	NA	≥2.0
Thyroid Function			
T ₃ Uptake, total	nmol/L	--	--
Reverse T ₃	nmol/L	--	--
Thyroxine (T ₄)	nmol/L	--	--
Human chorioic gonadotropin	IU/L	--	--
Free T ₄	pmol/L	--	--
Thyroid- stimulating hormone	mU/L	--	--
Follicle- stimulating hormone	--	--	--
Lipid Chemistry			
Total cholesterol	mg/dl	NA	≥300
LDL cholesterol	mg/dl	--	--
HDL cholesterol	mg/dl	--	--
Ratio (LDL/HDL)	Fraction	--	--
Triglycerides	mg/dl	NA	≥300

Parameter (Full Names)	Reporting Unit	Clinically Significant Criteria ¹	
		Low	High
Electrolytes			
Chloride	MEq/l	≤90	≥112
Potassium	MEq/l	≤3.0	≥5.8
Sodium	MEq/l	≤130	≥150
Bicarbonate	MEq/L	--	--
Metabolic			
Calcium	mg/dl	≤7.0	≥15.5
Phosphate	mg/dl	≤1.5	≥6.0
Blood Glucose	mg/dl	≤50 (fasting)	≥180 (fasting)
Uric Acid	mg/dl	NA	Male ≥10.5 Female ≥8.5
Cancer			
Prostate-specific antigen	--	--	--
Alpha-fetoprotein	--	--	--
Viral tests			
HIV	--	--	--
HIV ₂	--	--	--
Hepatitis A virus	--	--	--

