Hepatitis A antibody	--	--	--
Hepatitis B virus	--	--	--
Hepatitis B surface Antigen	--	--	--
Hepatitis B core antigen	--	--	--
Hepatitis C virus	--	--	--
Urinalysis			
(Urine) protein		NA	Increase≥2
(Urine) glucose		NA	Increase≥2
(Urine) bilirubin		NA	Increase≥2
Occult blood		NA	Increase≥2
Color		NA	Increase≥2
Ketone		NA	Increase≥2
Leukocyte esterase		NA	Increase≥2
pH		Decrease≥2	Increase≥2
Turbidity		NA	Increase≥2
Urobilinogen		NA	Increase≥2
Specific gravity		≤1.005	NA

¹ Can be revised as appropriate, but should be consistent within the project.

Parameter (Full Names)	Reporting Unit	Clinically Significant Criteria ¹	
		Low	High
Vital Sign			
Systolic blood pressure	mmHg	≤90 and ≥20 decrease	≥180 and ≥20 increase
Diastolic blood pressure	mmHg	≤50 and ≥15 decrease	≥105 and ≥15 increase
Pulse rate	bpm	≤50 and ≥15 decrease	≥120 and ≥15 increase
Body Temperature	C°	NA	≥1.11 C° Increase
Respiration rate	#/min	≤ 10	--
Height	cm	--	--
Weight	kg	≥7% decrease	≥7% increase
Body mass index	kg/m ²		
Hip Circumference	cm		
Waist Circumference	cm		
ECG			
Heart rate	bpm	<50	>100
R-R interval	msec	--	--
PR interval	msec	NA	>200 msec and >Baseline
QRS interval	msec	NA	>120 msec and >Baseline
QT interval	msec	NA	>450 and >30 increase
QTc interval	msec	<=350 and Baseline<375	>450 or >480 or >500 with Baseline <450
QTc interval ¹	msec	NA	>30 increase or >60 increase

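### SAP 10.1 flags temperature on rise alone, so the PCS count admits ordinary readings and can omit high ones; the high-calcium limit is probably too high to register a moderate rise

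*SAP*

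**What the plan says.** SAP 6.5 says that PCS abnormalities "will be defined according to the Akros Safety Reporting Standards as of 18 Oct, 2004", with the limits in SAP 10.1. They feed a table "presenting the number and percentage of subjects who had at least one PCS value on or after the first dose of study drug", which SAP 6.5.4 and 6.5.5 call for by treatment group.

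The rows at issue in SAP 10.1:

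- Calcium: "Calcium mg/dl ≤7.0 ≥15.5".
- Body temperature: no low criterion; high criterion "≥1.11 C° Increase", with no absolute level.

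The neighbouring vital-sign rows pair a level with a change: systolic pressure "≥180 and ≥20 increase", diastolic pressure "≥105 and ≥15 increase", pulse "≥120 and ≥15 increase". A footnote to the table says of the criteria: "Can be revised as appropriate, but should be consistent within the project".

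The documents give no calcium reference range, no temperature SD and no definition of fever.

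**The concern.** A PCS flag should pick out values that a safety reader would want to see. A rise-only temperature rule depends as much on the baseline reading as on the later one. A low baseline turns an ordinary later value into a flag, and a high-normal baseline can hide a high later value. The high-calcium limit raises a different doubt: it lies so far up that a moderate drug effect might leave no trace in that cell.

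The PCS table carries some weight here. For vital signs, SAP 6.5.5 plans descriptive statistics and PCS counts, and nothing else by arm. For laboratory tests, SAP 6.5.4 adds a second categorical table for liver tests only, plus frequencies for discrete urinalysis. Outside the adverse event tables, the PCS count is thus the only by-arm count of subjects with raised temperature or high calcium that the SAP specifies. Safety is a secondary objective, and protocol 1.3.2 names infection as a risk that the design sets out to reduce.

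**Working it through.** The plan gives no derivation for either cut-off, so there is no figure of its own to reproduce. The checks below apply the rules as written.

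**Inputs from the documents.** The two rows above; vital signs and biochemistry at six post-baseline visits (Visits 3 to 8, protocol Table 1); about 150 subjects, 50 per group (SAP 6.1).

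**Inputs assumed.** Temperature visit-to-visit SD 0.25 to 0.50 °C; calcium normal range from 8.5–8.8 to 10.0–10.5 mg/dL; calcium mean 9.2 to 9.8 and SD 0.35 to 0.8 mg/dL; 38.0 °C as an illustrative reference point only.

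**Temperature: the rule itself**

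- 1.11 × 1.8 = 2.0, so the criterion looks like a 2 °F change converted to Celsius.
- 37.1 − 35.9 = 1.2, which is at least 1.11: flagged.
- 38.4 − 37.4 = 1.0, which is below 1.11: not flagged.
- A reading of 38.0 °C is not flagged for any baseline of 36.9 °C or above (38.0 − 36.9 = 1.1). From a baseline of 35.5 °C, flags start at 35.5 + 1.11 = 36.61 °C.

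These results need no assumption about variability.

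**Temperature: flags by chance.** Take independent normal errors with SD *s* at baseline and at each of six visits, and no drug effect. Then

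P(at least one flag) = 1 − ∫ φ(b) · Φ(b + 1.11/s)⁶ db

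| Assumed SD (°C) | P(flag) | Subjects of 150 |
|---|---|---|
| 0.25 | 0.5% | 0.7 |
| 0.30 | 2.2% | 3.3 |
| 0.35 | 5.6% | 8.4 |
| 0.40 | 10.3% | 15.5 |
| 0.50 | 21.0% | 31.6 |

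A simulation with readings rounded to 0.1 °C (mean 36.6, between-subject SD 0.25, 0.25 and 0.30, within-subject SD 0.25, 0.35 and 0.45) flagged about 0.5, 7 and 21 of 150 subjects. In it, 93% to 98% of flagged readings were below 38.0 °C.

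**Calcium: distance from normal**

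- High side: 15.5/10.5 = 1.48 and 15.5/10.0 = 1.55, so 48% to 55% above the assumed ULN.
- Low side: 7.0/8.5 = 0.82 and 7.0/8.8 = 0.80, so 18% to 20% below the assumed lower limit.
- Midpoint of the two limits: (7.0 + 15.5)/2 = 11.25, above the assumed ULN. The chloride, potassium and sodium limits centre on (90 + 112)/2 = 101, (3.0 + 5.8)/2 = 4.4 and (130 + 150)/2 = 140.

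**Calcium: can the high side be reached?**

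- The limit lies between (15.5 − 9.8)/0.8 = 7.1 and (15.5 − 9.2)/0.35 = 18.0 SD above the assumed mean. Expected high flags among 150 × 6 = 900 values are below 10⁻⁹ from ordinary variation.
- For illustration, a drug that moved the mean from 9.5 to 11.5 with SD 0.5 would still leave the limit (15.5 − 11.5)/0.5 = 8 SD away.
- If extreme values truly occurred in 0.1% of subjects, the chance of none in 150 is 0.999¹⁵⁰ = 86%; at 1% it is 0.99¹⁵⁰ = 22%. An extreme event would be counted; a moderate rise would not.

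**The case against.** Several points count against a harsher reading, and most of them stand.

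- **Calcium is not the most distant limit in its section.** Fasting glucose at 180 mg/dL or more is 64% to 82% above an assumed ULN of 99 to 110 (180/110 = 1.64; 180/99 = 1.82). Male uric acid at 10.5 is 24% to 50% above an assumed ULN of 7.0 to 8.5. Distance from normal therefore does not prove a wrong digit. The off-centre midpoint fits a misprint, but only the 2004 standard could settle it.
- **A reader might infer that the calcium row will stay empty.** The documents do not support that. The low limit of 7.0 can be met, and an extreme high value would be counted.
- **Other outputs cover part of the gap.** Biochemistry and vital signs are described by visit and arm (SAP 6.5.4, 6.5.5), laboratory values are classed against the normal range (SAP 5.3.6), and listings flag out-of-range results (SAP 6.5). The cover is incomplete: means can hide a few outliers, and listings do not compare arms. Under protocol 3.6.1 an abnormal value becomes an adverse event only with symptoms, permanent discontinuation or a change in concomitant therapy, or if it is serious.
- **Temperature is not the only change-only row.** Weight, most urinalysis rows and the second QTc row are too. Still, a percentage weight change keeps its meaning without a level, while a temperature rise to an ordinary value does not.
- **A reader might infer that the temperature row would mostly count noise.** That rests on an SD that the documents do not give. At 0.25 °C the chance rate is only 0.5%, and chance flags should fall equally across randomized arms.

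**Conclusion.** The point holds as a minor one. The temperature defect follows from the rule as written: the PCS count includes rises that end at ordinary values and omits high readings from a high-normal baseline. How many chance flags result depends on the assumed SD (0.5% to 21% of subjects for 0.25 to 0.50 °C). The high-calcium limit is probably too high to register a moderate rise. That judgement rests on an assumed ordinary reference range, and a misprint is possible but not shown.

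It would go too far to say that either row cannot do its job. Both can return counts, and other safety outputs remain. What is weakened is the by-arm PCS count for two parameters. Nothing here touches the primary analysis, the error rate or any decision rule.

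**What to change.** Both changes concern analysis flags only and set no clinical rule.

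1. **Temperature.** Count any post-baseline value at or above an absolute level that the sponsor specifies before unblinding, whatever the baseline. Count a rise of 1.11 °C or more only when the reading also reaches a stated absolute level, as the blood pressure and pulse rows already do. The documents define no fever level, so the sponsor must supply these values.
2. **Calcium.** Check 15.5 mg/dL against the 2004 standard. Whether or not it proves a misprint, define the high limit relative to the laboratory ULN or by the CTCAE grades to which protocol 3.6.2 already refers.

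Cost: two cells in the appendix and the matching lines of code. The footnote to the table permits revision. The downside is that these rows would then differ from the 2004 standard, and the same footnote asks for consistency within the project, so the change may have to be carried into other JTE-451 studies.

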6.5.5 Vital Signs

Descriptive statistics of observed results and change from baseline for vital signs and body weight will be presented by time point and treatment group. Number and percentage of subjects with treatment-emergent PCS abnormal values will be presented by treatment group.

6.5.6 12-Lead ECG

Descriptive statistics of observed results and change from baseline will be presented by time point and treatment group for RR, PR, QRS, QT and QTcF intervals. The number and percentage of subjects with treatment-emergent PCS abnormal values will be presented by treatment group. Clinical interpretation of overall ECG findings will be summarized by time point and treatment group.

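### The low-QTc flag omits falls to 350 ms or below from a baseline of 375 ms or more, and the high-QTc flag does not say which thresholds its baseline clause governs.

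*SAP*

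**What the plan says.** The ECG block of SAP 10.1 has two QTc rows. The first sets absolute limits: low is "<=350 and Baseline<375" and high is ">450 or >480 or >500 with Baseline <450". The second sets a change limit on the high side only, ">30 increase or >60 increase", with no baseline condition; its low cell is marked not applicable.

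SAP 6.5 turns the table into an analysis rule: "Treatment-emergent PCS abnormalities are values that meet the specified criteria after the initiation of study drug". It adds that "The PCS values for vital signs, ECG and laboratory data will be flagged in data listings". SAP 6.5.6 then uses the rule for ECG: "The number and percentage of subjects with treatment-emergent PCS abnormal values will be presented by treatment group".

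Other rows of the same table treat baseline differently. PR is ">200 msec and >Baseline", and QRS has the same form with a limit of 120 ms. The low limits for pulse and for systolic and diastolic pressure each combine an absolute limit with a minimum fall from baseline.

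**The concern.** A treatment-emergent flag should pick out values that are abnormal and have worsened on treatment. The low-QTc cell instead requires the baseline to be already low, so for a given abnormal value it keeps the subjects who moved least and drops those who moved most.

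The high-QTc cell can be read in two ways. The baseline clause may attach only to the last threshold or to all three, and the two readings give different counts from the same data. The SAP also does not say whether the three thresholds form one flag or three lines of a table.

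At stake is the count by treatment group of subjects with marked QTc prolongation or shortening, in a trial with safety as a secondary objective. The mock tables are in a separate document (SAP 10.2), so these cells are the only programming rule a reader of the SAP can see.

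**Working it through.** The plan gives no figure to reproduce. The check applies the rules of SAP 10.1 to pairs of baseline value b and post-dose value q, in whole ms. The cases are illustrative, not trial data.

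**Low side.** Flag if q ≤ 350 and b < 375. For a fixed q, the largest flagged fall is 374 − q and the smallest unflagged fall is 375 − q.

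| q | Largest flagged fall | Smallest unflagged fall |
|---|---|---|
| 350 | 374 − 350 = 24 | 375 − 350 = 25 |
| 345 | 29 | 30 |
| 340 | 34 | 35 |
| 330 | 44 | 45 |

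- 420 to 345 (−75): not flagged.
- 380 to 348 (−32): not flagged.
- 352 to 349 (−3): flagged.
- 345 to 348 (+3, a rise): flagged.
- 374 to 300 (−74): flagged.

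The change row covers increases only, so it recovers none of the unflagged falls.

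**High side.**
- Reading A (clause governs only 500): q > 450, or q > 480, or (q > 500 and b < 450).
- Reading B (clause governs all three): b < 450 and (q > 450, or q > 480, or q > 500).
- Change row: q − b > 30.
- Separate line above 500, either reading: q > 500 and b < 450.

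| b to q | Change | Absolute row, A | Absolute row, B | Change row | Separate >500 line |
|---|---|---|---|---|---|
| 440 to 505 | +65 | yes | yes | yes | yes |
| 450 to 501 | +51 | yes | no | yes | no |
| 455 to 505 | +50 | yes | no | yes | no |
| 470 to 501 | +31 | yes | no | yes | no |
| 475 to 502 | +27 | yes | no | no | no |
| 495 to 505 | +10 | yes | no | no | no |

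Under reading A, no value above 500 escapes the row as a whole, because every such value is also above 450 and that threshold carries no condition. By the same logic, if A is a single flag, the 480 and 500 thresholds and the baseline clause add nothing.

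Under reading B, a value above 500 escapes both QTc rows when q ≥ 501, b ≥ 450 and q − b ≤ 30. That requires b ≥ 501 − 30 = 471.

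The uncorrected QT row, ">450 and >30 increase", does not fill the gap. It applies to a different measurement and also needs a rise of more than 30 ms.

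**The case against.** The strongest objection concerns the high side. A reader might infer that values above 500 ms go uncounted whenever baseline is 450 or more. The documents do not support that. If the clause governs only the 500 ms threshold, such values are flagged through the 450 ms threshold. If it governs all three, the change row still flags every rise above 30 ms. A table showing nobody above 500 ms when one occurred also presupposes a separate line for that category, which the SAP neither states nor rules out. All this stands, and it limits the high-side point to an ambiguity, a possible restriction of the >500 line and a narrow gap under one reading.

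Other safeguards also stand. SAP 6.5.6 summarises observed QTcF and change by visit, and SAP 6 includes the minimum and maximum in continuous summaries, so an extreme value at a scheduled visit would be visible. Unscheduled values appear in the listings. Overall ECG interpretation is tabulated, and ECG abnormalities that meet the conditions in Protocol 3.6.1 are recorded as adverse events. None of these, however, gives the number of subjects beyond a QTc limit by group, which is what the PCS table is for.

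Entry restrictions may make high baselines rare. Protocol 1.3.1 mentions cardiovascular restrictions, exclusion criteria 22 and 26 cover cardiac disease, and criteria 1 and 2 are redacted. No QTc limit is visible, so this can be neither confirmed nor dismissed.

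On the low side, it would go too far to say that the largest shortenings are always lost: 374 to 300 is counted. The visible text names no particular concern about QTc shortening. The rule still selects in the wrong direction at any given post-dose value.

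**Conclusion.** The low-QTc cell is wrong as written, and no reading rescues it. Any fall to 350 ms or below from a baseline of 375 or more is left out, which means a shortening of at least 25 ms, while trivial falls and even small rises from a low baseline are counted.

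The high-QTc cell is ambiguous. Under either reading, a >500 category tabulated on its own excludes every subject with a baseline of 450 or more. A value above 500 is missed by both QTc rows only if the clause governs all three thresholds, the baseline is 471 or more and the rise is 30 ms or less.

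Only the PCS flag and its n (%) table are affected. The primary analysis and sample size are untouched. The number of subjects concerned cannot be estimated, because the documents give no QTc distribution and two exclusion criteria are redacted. This should be corrected, but it does not threaten the trial's main conclusions.

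**What to change.** - **Low QTc:** replace the requirement for a baseline below 375 with a minimum decrease from baseline, in the form used for pulse and blood pressure. The sponsor has to set the size of the decrease; the documents give none. Simply deleting the baseline condition would still flag 352 to 349.
- **High QTc:** tabulate values above 450, 480 and 500 separately. Keep the baseline limit of 450 only for the new-onset category above 450. Count post-baseline QTcF above 480 and above 500 whatever the baseline, provided the value exceeds baseline, as the PR and QRS rows require. Then 475 to 502 is counted and 505 to 502, a fall, is not.

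The cost is an edit to two cells and the matching program and mock table; no new data are needed. A few more subjects with a high baseline will be flagged. The table's footnote allows revision but asks for consistency within the project, and SAP 6.5 takes the criteria from a sponsor standard, so the change has to be carried through the project and not made in this SAP alone.

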10.2 Mock Summary Tables

The mock summary tables will be created in a separate document.

10.3 Mock Data Listings

The mock summary listings will be created in a separate document.

10.4 Mock Figures

The mock summary figures will be created in a separate document.

¹ Can be revised as appropriate, but should be consistent within the project.
